3.2 Leukapheresis

Before leukapheresis, the following assessments should be completed:

- Vital signs (including pulse oximetry)
- Concomitant medications
- CBC

After leukapheresis, the following assessments should be completed:

- Adverse event review and evaluation
- CBC

3.3 Management of Possible Toxicities

All toxicities should be managed based on institutional guidelines and per apheresis physician's discretion. Below are recommendations and deviations from them will not be considered as protocol deviation.

3.3.1 Hypocalcemia

Hypocalcemia is a decrease in calcium levels. Hypocalcemia is a response to citrate toxicity, which can result with large volume leukapheresis. Symptoms of hypocalcemia include numbness and tingling, especially in the hands, feet, and around the mouth. Hypocalcemia can also cause painful muscle spasms that can be alleviated with calcium-rich foods and supplements. If symptoms persist during the procedure, the following protocols are advised: slowing the procedure, decreasing the amount of anticoagulation, and administering oral or intravenous calcium supplementation.

3.3.2 Vasovagal Response

Few subjects experience episodes of vasovagal responses such as lightheadedness or fainting. These occurrences are induced by extracorporeal blood flow and discomfort and/or fear of venipunctures. Major vasovagal episodes have been reported from patients receiving therapeutic leukapheresis in research for treatment of polymyositis and dermatomyositis, diseases of the muscle tissue.

3.3.3 Blood Loss

Varying, minor degrees of RBC or platelet loss have been reported. Devices separate and return blood according to different manufacturer settings that may have an influence on accounted hemoglobin or hematocrit levels. Significant blood loss, however, has not been reported. Patients with a history of anemia or thrombocytopenia should proceed leukapheresis treatments with caution.

3.3.4 Discomfort at Venipuncture Site

Discomfort, bruising, bleeding, or swelling at the venipuncture site may occur. These minor interactions may occur with any venipuncture procedure and is usually dependent on venous

structural integrity. Routine procedures are in place at each facility to help minimize the occurrence of these discomforts and, in some cases, an alternate venipuncture site may be utilized.

3.3.5 Infection

Infection, although rare, can occur at the venipuncture site due to cannula or catheter placement. Infection is minimized with proper sterilization standards and has been significantly reduced with disposable collection and storage equipment.

4 Safety, Adverse Events, Protocol Deviation and Stopping Rules

4.1 Definitions

4.1.1 Adverse Events (AE)

An adverse event (AE) is defined as any reaction, side effect, or untoward event that occurs during the clinical trial associated with the use of a test article in humans, whether or not the event is considered related to the treatment or clinically significant. For this study, AEs will include events reported by the patient, as well as clinically significant abnormal findings on physical examination or laboratory evaluation. A new illness, symptom, sign or worsening of a pre-existing condition or abnormality is considered an AE. An abnormal laboratory value will be considered an AE if the laboratory abnormality is characterized by any of the following:

- Results in discontinuation from the study
- Is associated with clinical signs or symptoms
- Requires treatment or any other therapeutic intervention
- Is associated with death or another serious adverse event, including hospitalization.
- Is judged by the Investigator to be of significant clinical impact

All AEs, including clinically significant abnormal findings on laboratory evaluations, regardless of severity, will be followed until satisfactory resolution.

4.1.2 Suspected Adverse Reaction

Suspected adverse reaction means any adverse event for which there is a reasonable possibility that the test article caused the adverse event. For the purposes of IND safety reporting, "reasonable possibility" means there is evidence to suggest a causal relationship between the test article and the adverse event. A suspected adverse reaction implies less certainty about causality than adverse reaction, which means any adverse event caused by a test article.

4.1.3 Serious Unexpected Adverse Reaction (SUSAR)

An adverse event or suspected adverse reaction is considered "unexpected" if it is not listed in the investigator brochure or is not listed at the specificity or severity that has been observed; or, if an investigator brochure is not required or available, is not consistent with the risk information described in the general investigational plan or elsewhere in the current application. "Unexpected"

also refers to adverse events or suspected adverse reactions that are mentioned in the investigator brochure as occurring with a class of the test article or as anticipated from the pharmacological properties of the drug but are not specifically mentioned as occurring with the test article under investigation.

4.1.4 Serious Adverse Event (SAE)

An adverse event or suspected adverse reaction is considered serious if in the view of the investigator or the sponsor, it results in any of the following:

- Persistent or significant incapacity or substantial disruption of the ability to conduct normal life functions
- A congenital anomaly/birth defect
- Important medical events that may not result in death, be life-threatening, or require hospitalization may be considered a SAE experience when, based upon appropriate medical judgment, they may jeopardize the patient or subject and may require medical or surgical intervention to prevent one of the outcomes listed in this definition.

4.1.5 Protocol Deviation

A one-time, unintentional action or process that departs from the IRB-approved study protocol, involving one incident and identified retrospectively, after the event occurred. Any leukapheresis-related failure or deviation will be recorded, even if it does not constitute a per-protocol AE.

4.2 Recording of Adverse Events

4.2.1 Adverse Event Recording Period

The study period during which adverse events must be reported is normally defined as the period from the signing of consent to the leukapheresis completion. Serious Adverse Event reporting period starts with leukapheresis and ends 72 hours after the procedure.

All unresolved adverse events should be followed by the investigator until the events are resolved, the subject is lost to follow-up, or the adverse event is otherwise explained. At the last scheduled visit, the investigator should instruct each subject to report any suspected adverse event(s) that might reasonably be related to participation in this study. The investigator should notify the Sponsor of any death or adverse event occurring at any time after a subject has discontinued or terminated study participation if the event may reasonably be related to this study. The Sponsor should also be notified if the investigator should become aware of the development of cancer or of a congenital anomaly in a subsequently conceived offspring of a subject that has participated in this study.

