5.1.4 Serious Adverse Event (SAE)

An adverse event or suspected adverse reaction is considered serious if in the view of the investigator or the sponsor, it results in any of the following:

- Death within 30 days of Descartes-11 infusion
- Grade 4 or 5 CRS, infusion reaction, neurotoxicity
- Inpatient hospitalization or prolongation of existing hospitalization (except for protocol-mandated ~24-hour admission for observation due to new-onset fever)
- Persistent or significant incapacity or substantial disruption of the ability to conduct normal life functions
- A congenital anomaly/birth defect
- Important medical events that may not result in death, be life-threatening, or require hospitalization may be considered a SAE experience when, based upon appropriate medical judgment, they may jeopardize the patient or subject and may require medical or surgical intervention to prevent one of the outcomes listed in this definition.

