5.2 Recording of Adverse Events

5.2.1 Adverse Event Recording Period

The study period during which adverse events must be reported is normally defined as the period from the initiation of any study procedures to the protocol therapy completion. For this study, collection of adverse events will begin with enrollment until the subject is off-study. Serious Adverse Event reporting period starts with leukapheresis and ends at 30 days after last Descartes-11 infusion.

All unresolved adverse events should be followed by the investigator until the events are resolved, the subject is lost to follow-up, or the adverse event is otherwise explained. At the last scheduled visit, the investigator should instruct each subject to report any suspected adverse event(s) that might reasonably be related to participation in this study. The investigator should notify the Sponsor of any death or adverse event occurring at any time after a subject has discontinued or terminated study participation if the event may reasonably be related to this study. The Sponsor should also be notified if the investigator should become aware of the development of cancer or of a congenital anomaly in a subsequently conceived offspring of a subject that has participated in this study.

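### The SAE definitions do not match the SAE reporting windows: death before first infusion, and life-threatening events generally, are not listed as serious

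*Combined protocol and SAP*

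**What the plan says.** **Windows.** In the collection protocol (Appendix B, 4.2.1), adverse-event reporting is "normally defined as the period from the signing of consent to the leukapheresis completion", and the "Serious Adverse Event reporting period starts with leukapheresis and ends 72 hours after the procedure". In the main protocol (5.2.1), the "Serious Adverse Event reporting period starts with leukapheresis and ends at 30 days after last Descartes-11 infusion".

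**Deadlines.** Main 5.2.5 and Appendix B, 4.2.5 require every SAE and SUSAR to reach the sponsor within 24 hours, whatever the suspected cause. Other adverse events are entered in the eCRF within 10 working days (main 5.2.4; Appendix B, 4.2.4).

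**Definitions.** Appendix B, 4.1.4 lists "Persistent or significant incapacity or substantial disruption of the ability to conduct normal life functions", congenital anomaly, and a catch-all for important medical events. The catch-all applies by medical judgment to events that could endanger the patient and "may require medical or surgical intervention to prevent one of the outcomes listed in this definition". Main 5.1.4 has the same entries plus "Death within 30 days of Descartes-11 infusion", "Grade 4 or 5 CRS, infusion reaction, neurotoxicity", and inpatient hospitalization. Neither list has a general criterion for life-threatening events.

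**Signs of intent.** Appendix B, 4.1.1, in describing when a laboratory abnormality is an adverse event, says "Is associated with death or another serious adverse event, including hospitalization". That wording treats death and hospitalization as serious.

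**The concern.** Both documents start the SAE window at leukapheresis, so both mean to capture serious events around collection. The definition decides what is reported within 24 hours. If it leaves out the gravest outcomes, the window does little for them.

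Patients at risk are those collected and waiting for product. The main protocol measures death from an infusion, and a patient who dies before the first infusion has none to measure from. Under main 2.2.4 that patient counts as a premature discontinuation. The reason goes on the case report form, but that section sets no 24-hour deadline.

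The missing life-threatening criterion also matters after infusion. Main 5.5 pauses the study when two subjects have Grade 4 vital-organ events probably or definitely related to the study drug within 14 days after the last infusion. A Grade 4 organ toxicity handled without admission could count toward that pause, yet its 24-hour report would depend on the investigator choosing to apply the catch-all.

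**Working it through.** No figure in the plan needs reproducing. The check sets each type of event against each definition.

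| Event | Appendix B, 4.1.4 | Main 5.1.4 | Other provision |
|---|---|---|---|
| Death after leukapheresis, before first infusion | Not listed | Not listed; criterion is tied to an infusion | IRB report of deaths on study; sponsor notice of reasonably related deaths after participation ends, with no deadline |
| Life-threatening event in the same interval, no admission | Catch-all only | Catch-all only | Routine adverse-event entry |
| Hospitalization | Not listed | Listed | Appendix B, 4.2.2 makes it an SAE |
| Post-infusion life-threatening event other than the three named types, no admission | Outside the collection window | Catch-all only | Routine adverse-event entry |
| Death from first infusion to 30 days after the last | Outside the collection window | Listed | None needed |

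**1. Where the death gap lies.** Infusions are planned for Days 1, 4, 8, 11, 15 and 18 (main 3.2.1). The death criterion therefore runs without a break from Day 1 to Day 18 + 30 = Day 48, the end of the main SAE window. On the planned schedule the mismatch is confined to the time before Day 1.

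**2. Whether the catch-all closes it.** It is discretionary, and it concerns events needing intervention to prevent an outcome on the list. Death is not on the Appendix B list. In the main list, death appears only in relation to an infusion.

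**3. Whether the cross-reference closes it.** Appendix B, 4.2.4 refers to Section 5.1 for seriousness. Within Appendix B that section is General Issues. If the main protocol's 5.1 is meant, hospitalization is imported, but a death before infusion is still unlisted.

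**4. Whether the SUSAR route closes it.** Before infusion it cannot apply: main 5.1.2 ties a suspected reaction to the test article, and none has been given. After infusion it does not clearly help, because the term itself requires seriousness and main 5.1.3 defines only what is unexpected.

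**5. The difference in timing.** Ten working days, ignoring holidays, is 14 calendar days for an event known on Monday to Friday, 13 for Saturday and 12 for Sunday. Against 24 hours the difference is 12 - 1 = 11 to 14 - 1 = 13 days. This takes eCRF entry as the point at which the sponsor can first see the event.

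**The case against.** The best counter-argument is that, read as a whole, the text already treats death as serious. Appendix B, 4.1.1 speaks that way, and Appendix B, 4.2.4 exempts fatal progression of malignancy from SAE reporting, which would be pointless unless other deaths were SAEs. This shows what the authors intended, but neither place makes death a criterion, and the mismatch between main 5.1.4 and main 5.2.1 remains whichever document governs.

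A second argument is that a life-threatening event plainly endangers the patient, so any sensible investigator would use the catch-all, and many such events lead to admission and are SAEs for that reason. That is true in practice and keeps the matter small. What remains is death without admission and life-threatening events treated without admission.

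Some stronger readings are tempting but unsupported:

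- *Hospitalization goes unreported after collection.* It does not, because Appendix B, 4.2.2 makes it an SAE, with stated exceptions. Its absence from 4.1.4 is only an inconsistency.
- *Nothing is covered after 72 hours.* Appendix B, 4.2.1 asks for notice of reasonably related deaths and events at any time after participation ends, Appendix B, 4.2.5.2 sends deaths to the IRB, and main 5.2.1 keeps the SAE window open for enrolled subjects. Appendix B, 2.3.1 says those referred for collection are enrolled.
- *Appendix B wrongly drops the Grade 4-5 criterion.* That criterion names toxicities of the infused product and has no place in a collection protocol.
- *The sponsor would miss the 7-day FDA deadline.* Main 5.2.5.3 applies that interval to suspected adverse reactions. Before infusion no Descartes-11 has been given, so no overrun can be claimed.

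**Conclusion.** The definitions are wrong as written, and the severity is minor. A death or life-threatening event between leukapheresis and first infusion, as such, meets no explicit SAE criterion in either document. Nor does a post-infusion life-threatening event outside the three named types when managed without admission. For these the 24-hour report depends on judgment, and the routine alternative is 11 to 13 days slower. A death judged unrelated is the weakest case: the related-event notice does not cover it, although SAE reporting is meant to apply regardless of cause.

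Up to 34 planned patients are exposed, plus any who are collected and never infused. The documents give no event rate, and Appendix B, 3.3 describes the procedure's risks as mostly minor or rare, so few events are expected. Most investigators would probably report a death promptly anyway. The primary endpoint is not affected.

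The Appendix B part assumes that the published list in 4.1.4 is complete; it shows no redaction or gap. The main-protocol part does not depend on this.

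**What to change.** - **Appendix B, 4.1.4:** add death, a life-threatening event, and inpatient hospitalization or its prolongation. The last brings the definition into line with Appendix B, 4.2.2.
- **Main 5.1.4:** replace the death criterion with *Death from the start of leukapheresis to 30 days after the last Descartes-11 infusion*, so that it matches the window in 5.2.1, and add *A life-threatening event*.
- **Keep** the exclusion for progression of malignancy in main 5.2.4 and Appendix B, 4.2.4.

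This adds three criteria to one list and makes two edits to the other, with no new visits or tests. The downside is a few more SAE forms, including some for events unrelated to collection or to the product.

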4.2.2 Hospitalization, Prolonged Hospitalization or Surgery

Any adverse event that results in hospitalization or prolonged hospitalization should be documented and reported as a serious adverse event unless specifically instructed otherwise as below. Any condition responsible for surgery should be documented as an adverse event if the

condition meets the criteria for an adverse event. Neither the condition, hospitalization, prolonged hospitalization, nor surgery are reported as an adverse event in the following circumstances:

- Hospitalization or prolonged hospitalization for diagnostic or elective surgical procedures for a preexisting condition. Surgery should not be reported as an outcome of an adverse event if the purpose of the surgery was elective or diagnostic and the outcome was uneventful.
- Hospitalization or prolonged hospitalization for therapy of the target disease of the study, unless there is clinical worsening or an increase in frequency of hospital admissions as judged by the clinical investigator.

4.2.3 Pregnancies

To ensure patient safety, each pregnancy in a patient on study treatment must be reported to the Sponsor within 24 hours of learning of its occurrence. The pregnancy must be followed up to determine outcome, including spontaneous or voluntary termination, details of the birth, and the presence or absence of any birth defects, congenital abnormalities, or maternal and/or newborn complications. Pregnancy should be recorded on a Clinical Study Pregnancy Form and reported by the investigator to the Sponsor. Pregnancy follow-up should be recorded on the same form and must include an assessment of the possible relationship to the study treatment of any pregnancy outcome. Any SAE experienced during pregnancy must be reported on the SAE Report Form. Pregnancy outcomes must be collected for the female partners of any males who took study treatment in this study. Consent to report information regarding these pregnancy outcomes should be obtained from the mother.

4.2.4 Recording of Adverse Events

Information on all adverse events should be recorded immediately in the source document, and in the appropriate adverse event module of the case report form (CRF). All clearly related signs, symptoms, and abnormal diagnostic procedures results should be recorded in the source document, though should be grouped under one diagnosis. To the extent possible, adverse events should be recorded as a diagnosis and symptoms used to make the diagnosis recorded within the diagnosis event. Do not list symptoms if a diagnosis can be assigned.

Adverse events (including lab abnormalities that constitute AEs) should be described using a diagnosis whenever possible, rather than individual underlying signs and symptoms. When a clear diagnosis cannot be identified, each sign or symptom should be reported as a separate Adverse Event. The clinical course of each event should be followed until resolution, stabilization, or until it has been determined that the study treatment or participation is not the cause. As detailed as possible, each adverse event should be evaluated to determine:

- The severity grade (CTCAE Version 5.0 Grade 1-5)
- Its duration (start and end dates)
- Its relationship to the leukapheresis procedure Is there a reasonable possibility that the AE is related to procedure- No (unrelated) or Yes. If yes- is the event definitely, probably, possibly or unlikely related

- Action taken with respect to study or investigational treatment (none, dose adjusted, temporarily interrupted, permanently discontinued, unknown, not applicable)
- Whether medication or therapy taken (i.e., no concomitant medication/non-drug therapy, concomitant medication/non-drug therapy)
- Whether it is serious, as defined in [Section 5.1](#).

All adverse events should be treated appropriately. If a concomitant medication or non-drug therapy is given, this action should be recorded on the Adverse Event CRF. Adverse events should be entered into the eCRF system within 10 working days from the knowledge of the event took place. Once an adverse event is detected, it should be followed until its resolution or until it is judged to be permanent, and assessment should be made at each visit (or more frequently, if necessary) of any changes in severity, the suspected relationship to the study treatment, the interventions required to treat it, and the outcome.

Progression of malignancy (including fatal outcomes), documented appropriately in the medical records, should not be reported as a serious adverse event. Adverse events that occur concurrently with the progression of malignancy but that are not related to disease progression (i.e., deep vein thrombosis) will be reported as an adverse event as described above.

4.2.5 SAE and SUSAR Reporting

To ensure patient safety, every SAE and SUSAR, regardless of suspected causality, occurring during the adverse event reporting period must be reported to the Sponsor within 24 hours of learning of its occurrence. Recurrent episodes, complications, or progression of the initial SAE must be reported as follow-up information is received. An SAE occurring at a different time interval or otherwise considered completely unrelated to a previously reported one should be reported separately as a new event.

4.2.5.1 Study Sponsor Notification by the Investigator

Any SUSAR and SAE as defined in [Section 4.1](#) must be reported to the Sponsor by **email or fax within 24 hours** of knowledge of the event. To the extent possible, adverse events should be recorded as a diagnosis. Do not list symptoms if a diagnosis can be assigned. At the time of the initial notification, a serious adverse event (SAE) report form should be filled. Following parameters will be asked in the form:

- Subject information
- A description of the event (if there is a diagnosis, it should be included)
- Date of onset
- Current status
- Whether study treatment was discontinued
- The reason why the event is classified as serious
- Investigator assessment of the association between the event and procedure
- Concomitant medications when the event happened
- Narrative summary of the event

Follow-up information on this event should be reported when received. The follow-up information should describe 1) whether the event has resolved or continues, 2) if and how it was treated, and 3) whether the patient continued or withdrew from study participation.

